The first onset of GI irAEs generally occurred within the first 12 weeks of treatment and was generally reversible. Bowel wall biopsies demonstrated a pleomorphic infiltrate, including many lymphocytes, consistent with colitis due to an autoimmune process. In addition, upper GI tract involvement including ileitis, duodenitis, and esophagitis have been reported.

- **Gastrointestinal perforation in association with narcotic use:** Isolated cases of intestinal perforation in association with narcotic use have been reported. The use of narcotics may potentially mask GI symptoms or delay detection of their relevant complications, such as bowel perforation.
- **Inflammatory Hepatotoxicity:** Immune-related hepatic dysfunction, including hepatitis or abnormal liver function tests (LFTs) attributed to ipilimumab therapy, has been reported. Subjects may develop elevations in LFTs in the absence of clinical symptoms. Inflammatory hepatotoxicity includes non-infectious hepatitis (e.g., autoimmune hepatitis). Hepatic irAEs generally occur in the first 12 weeks of treatment and are primarily reversible (see hepatotoxicity management algorithm in Appendix 5).
- **Hypophysitis/Hypopituitarism and Other Endocrine Conditions:** Hypophysitis/hypopituitarism, clinically manifested by fatigue, has been reported. Most subjects with hypopituitarism presented with nonspecific complaints such as fatigue, confusion, visual disturbance, or impotence. Some had headache as the predominant presentation. The majority of subjects with hypopituitarism demonstrated enlarged pituitary glands based on brain magnetic resonance imaging. Low adrenocorticotrophic hormone and cortisol were the most common biochemical abnormality reported; low thyroid stimulating hormone, testosterone, or prolactin was also reported in some subjects.⁵⁰ The first onset of endocrine irAEs typically occurred between weeks 6 and 12 of treatment. Hypophysitis/hypopituitarism was controlled with appropriate hormone replacement therapy and may be dose related. Other endocrine glands may be targets of ipilimumab-related toxicity, and rare cases of primary adrenal insufficiency, hyperthyroidism and hypothyroidism were reported (see endocrinopathy management algorithm in Appendix 6).

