Treatment related serious adverse events (SAEs) were reported in 49% of patients in the combination treated subjects (N = 53) and most frequently severe SAEs were: AST elevation (13.2%), ALT elevation (11.3%), lipase elevation (5.7%) and diarrhea, colitis and renal failure (3.8% each). Ten of the 53 (18.9%) treated subjects in the combination cohort

discontinued therapy due treatment-related adverse events, the most frequent of which were ALT, AST elevation, lipase elevation, renal failure or pneumonitis. No drug-related deaths were reported. Median time to event onset was approximately 61 days (range: 4 to 114 days).

Immunotherapy and Breast Cancer:

The interrelationship between the tumor, the tumor microenvironment and the function of infiltrating immune cells at the tumor site, is important for generating efficacious anti-tumor immune response (Naito 1998). It is also well established that the magnitude of the tumor burden leads to local suppression and apoptosis of the infiltrating T-Cells.³⁷ In breast cancer, the influence of tumor burden on the generation of tumor antigen-specific cytotoxic T-lymphocytes (CTLs) was investigated in a phase I/II clinical trial in the metastatic setting. The study evaluated the cytotoxic function in an adoptive immunotherapy model in 2 patient study arms, one with macroscopic disease and other with a complete remission (CR). The results revealed that the cytotoxic function was sustained in only one CR patient, suggesting that tumor burden had an inverse effect on the function of the generated CTLs.³⁸

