4.2 Intervention

During study intervention planning, the standard of care for patients with early stage primary breast cancer diagnosis and treatment of as well as the timing of the definitive surgery schedule will not be altered in any way for patients participating in this study. If a patient experiences side effects from intervention resulting in a delay of their planned surgery date, this will be a failure of the primary endpoint. The planned intervention of this study is to obtain image guided biopsies, percutaneous MRI or US guided breast tumor cryoablation, and ipilimumab/nivolumab administration.

Most patients will have an outside biopsy confirming the diagnosis of breast cancer at the time of the initial surgical consultation. However, because the cryoablation procedure will cause near complete tumor destruction (that in turn will cause immunologic effect and antitumor response), pre-cryoablation breast biopsies will be performed. At least three 18G MRI or US-guided core biopsies of the primary breast tumor will be obtained (together with core biopsies of any suspicious lymph nodes as clinically or radiographically indicated) if feasible. Two core breast specimens will be provided to the MSKCC Breast and Imaging Center (BAIC) pathology department for routine (standard of care) testing. Additional core biopsy specimens will be sent to the immune monitoring facility (IMF) for research purposes as detailed in section 12. If not all three core biopsies can be performed, this will not make the patient ineligible.

The MRI or US-guided biopsies will be performed by investigators from the Breast Radiology Service with the assistance of investigators from Interventional Radiology and Anesthesiology as needed. Image guided percutaneous cryoablation can be performed through a small nick making it a minimally invasive procedure that has been performed safely in cancer patients for many years. The cryoablation will be performed 7-10 days prior to the surgery date.

Ipilimumab and nivolumab are fully human, monoclonal anti-CTLA4 antibodies that have shown anti-tumor activity and are now US FDA approved for the treatment of patients with unresectable advanced melanoma (unresectable stage III or stage IV).

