Recent studies have shown that administration of ipilimumab in the pre-operative setting is safe and does not cause delay of surgery in bladder cancer.¹² In this study, ipilimumab and Nivolumab will be administered 1-5 days prior to core biopsy + cryoablation and 8-15 days prior to the planned surgery.

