9.0 TREATMENT/INTERVENTION PLAN

Patients will undergo breast biopsy with cryoablation 7-10 days prior to the planned surgery, and ipilimumab with nivolumab administration 1-5 days before cryoablation. All patients will undergo surgery at the pre-determined day defined at the initial surgical consultation as detailed in section 4.1.

9.1 Ipilimumab and Nivolumab:

Women will receive ipilimumab and nivolumab 1-5 days prior to US or MRI-guided core biopsy and cryoablation date. Intravenous ipilimumab will be administered as a single 1 mg/kg dose to be infused intravenously over 90 minutes in the chemotherapy suite of the BAIC. Intravenous nivolumab will be administered as a single 3 mg/kg dose to be infused intravenously over 60 minutes in the chemotherapy suite of the BAIC.

In a study reported by [name] of various doses of ipilimumab and nivolumab in combination in metastatic melanoma, there was a 98% AE rate, a 93% treatment related AE rate, a 72% grade 3/4 AE rate, a 53% treatment related grade 3/4 AE rate and a 49% serious AE rate.⁶¹ Toxicity with both drugs administered at 3mg/kg was considered unacceptable, and nivolumab at 1mg/kg with ipilimumab at 3mg/kg was considered the maximum dose with an “acceptable” level of AEs - a threshold which is unlikely to be “acceptable” in the curative setting. Thus, combination therapy with ipilimumab administered at 1mg/kg and nivolumab administered at 3mg/kg was recommended and will be the dose we will administer for this study.

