14.0 BIOSTATISTICS

Definitive surgery confers cure for many women with early stage breast cancer and it is therefore imperative that any experimental pre-operative therapeutic innovation not undermine the timing of curative-intent surgery. Consequently, the primary endpoint for this study is safety/tolerability, as defined by the number of patients who do not develop grade 3 or 4 adverse events that necessitates a delay in surgery. Therefore, if 5 or 6 of the 6 patients are without an AE necessitating delay in surgery, the regimen will be considered safe/tolerable for further study. The probability of observing 5 or 6 patients (out of 6) who for whom therapy is safe/tolerable is 0.53 if the true safety/tolerability rate is 0.75, 0.65 if the true safety/tolerability rate is 0.80, and 0.89 if the true safety/tolerability rate is 0.90. This rule is based on the time period from start of the investigation regimen to the date of surgery, which is estimated to be approximately 15 days. Safety data up to 12 weeks following surgery will also be evaluated and reported.

Study design and analysis of the data will be performed with the assistance of [name], Division of Epidemiology and Biostatistics.

This is a pilot study using innovative methods and if cryoablation and single-dose ipilimumab/nivolumab is deemed safe, will result in the design of a larger trial. As such, there is no formal statistical analysis or sample size calculation for this study. All analysis will be descriptive in nature and the sample size is dictated by drug availability and budget constraints.

We have several exploratory secondary analyses. As noted above, all analyses will be evaluated descriptively and graphically. Serum and tumor biomarker levels (including lymphocytes and DC's) and serum cytokines will be plotted over the study timepoints. The ratio of specific intra-tumoral and serum t cell populations (i.e. CD4+FOXP3+ T-regulatory cells (Tregs) to CD8+Effector cells) will also be plotted over study timepoints. Other endpoints that will be summarized descriptively include ALC, and absolute T cell count.

Estimated accrual will be approximately 2-3 patients per month, making targeted completion of accrual within approximately 2 to 3 months of the study initiation.

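### The 5-of-6 rule closes at surgery, 8 to 15 days after dosing: it can show that surgery is not delayed, but not by itself that the regimen is safe and tolerable

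*Combined protocol and SAP*

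**What the plan says.** The primary objective in Section 2.0 is the safety and tolerability of the pre-operative regimen. Sections 1.0, 12.1 and 14.0 each decide it in the same way: with at least 5 of 6 patients free of an adverse event that forces a delay in surgery, the regimen counts as safe/tolerable and may go forward. Section 14.0 adds that a finding of safety leads to a larger trial.

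On the window, Section 14.0 states: "This rule is based on the time period from start of the investigation regimen to the date of surgery". The length of that period is then given in these words: "which is estimated to be approximately 15 days". Section 4.2 schedules the drugs "1-5 days prior to core biopsy + cryoablation and 8-15 days prior to the planned surgery". The parts are consistent with that total: "The cryoablation will be performed 7-10 days prior to the surgery date" (Section 4.2) and "ipilimumab with nivolumab administration 1-5 days before cryoablation" (Section 9.0).

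On later safety, Section 12.1 has adverse events tabulated and reviewed up to 12 weeks after drug administration. Section 14.0 says that safety data to 12 weeks after surgery will be evaluated and reported. Neither section links these data to the 5-of-6 conclusion.

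On onset, Section 3.0 says of endocrine events: "The first onset of endocrine irAEs typically occurred between weeks 6 and 12 of treatment". It places gastrointestinal and hepatic immune events generally within the first 12 weeks. For the combination in melanoma it reports: "Median time to event onset was approximately 61 days (range: 4 to 114 days"). The same section argues that immune-related events usually follow several doses of ipilimumab and are unlikely after the single dose given here.

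**The concern.** Whether the regimen delays curative surgery is a justified primary question, and Section 14.0 explains why. It is narrower than safety and tolerability. An adverse event that begins after surgery cannot delay surgery, so under the rule it cannot count against the regimen, whatever its grade. Six of six could pass, and the regimen be declared fit for a larger trial, with several women having grade 3 or 4 immune events in the following weeks. Those events would be in the report but not in the basis for the conclusion.

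A second, smaller matter is that Section 14.0 describes the window by a single figure that the schedule allows only as its upper limit. A reader would take the time at risk to be longer, and more uniform across patients, than the schedule provides.

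**Working it through.** **1. The plan's own figures.** With 6 patients and a true rate p of no surgery-delaying event, the chance of passing is P = 6p⁵(1−p) + p⁶.

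- p = 0.75: 0.35596 + 0.17798 = 0.534 (plan: 0.53)
- p = 0.80: 0.39322 + 0.26214 = 0.655 (plan: 0.65, apparently truncated)
- p = 0.90: 0.35429 + 0.53144 = 0.886 (plan: 0.89)

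All three reproduce. The length of the window is not an input, so correcting it changes none of them.

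**2. The window.** Inputs are drugs 1 to 5 days before cryoablation and cryoablation 7 to 10 days before surgery.

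- Shortest: 1 + 7 = 8 days
- Longest: 5 + 10 = 15 days
- Midpoint: (8 + 15)/2 = 11.5 days
- Ratio of longest to shortest: 15/8 = 1.9

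Of the 5 × 4 = 20 whole-day schedules, only one (5 + 10) gives 15 days. That is a count of permitted schedules, not a forecast of where the six patients will fall.

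**3. The window against the onset times quoted in Section 3.0.**

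| Event class | Onset as described | Relation to a window closing on day 8 to 15 |
|---|---|---|
| Endocrine immune events | Typically weeks 6 to 12 (days 42 to 84) | Begins at least 42 − 15 = 27 days after the window closes |
| Gastrointestinal and hepatic immune events | Generally within the first 12 weeks | Partly inside, partly outside; no split given |
| Combination events, melanoma, repeat dosing | Median about 61 days, range 4 to 114 | Median is 61 − 15 = 46 days after the longest window closes |

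The protocol's own account therefore places at least one class of event typically after the rule has closed, and lets two others fall on either side.

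**4. The later follow-up.** Section 12.1 ends it at 12 × 7 = 84 days after the drugs. Section 14.0 ends it 84 days after surgery, which is 84 + 8 = 92 to 84 + 15 = 99 days after the drugs. The schema in Section 1.0 (at least 12 weeks) and Appendix 1 both count from the drugs. The two end points differ by 8 to 15 days, and neither reaches the quoted upper range of 114 days.

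**The case against.** The case on the other side is substantial.

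- **The window is defined by events, not by a number.** It runs from start of regimen to surgery, and 15 days is offered only as an estimate. The exact intervals stand elsewhere in the protocol, and no patient would be classified differently. This stands: the correction is editorial.
- **The protocol defines its own term.** Section 14.0 says openly that safety/tolerability here means no surgery-delaying event, and limits the consequence to further study after a descriptive pilot. Section 12.1 has all adverse events reviewed for clinical importance to 12 weeks. This stands in part. Later events are not ignored, but the stated rule reaches its conclusion without them, and the label will be read more widely than the definition.
- **Immune events may be rare after one dose.** Section 3.0 argues this for ipilimumab. The argument must be weighed, though it does not address the combination and gives no onset times after a single dose.

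A reader might also infer that some 90% or more of toxicity falls outside the window. The documents do not support that. The 61-day median comes from repeat dosing in advanced melanoma, and the text does not say which events it describes. The share also depends on an assumed shape. A straight line from day 4 to the median puts 0.5 × (8 − 4)/(61 − 4) = 3.5% of onsets by day 8 and 0.5 × (15 − 4)/(61 − 4) = 9.6% by day 15. An exponential with the same median puts 1 − 2^(−8/61) = 8.7% and 1 − 2^(−15/61) = 15.7%. Neither covers infusion reactions, which Section 3.0 expects mostly within 24 hours, or the complications of cryoablation.

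Nor does the protocol say that severe immune events in general usually occur after surgery. Only endocrine events are placed specifically at weeks 6 to 12.

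**Conclusion.** The point holds in a limited form. The approximate 15 days is the upper end of an 8-to-15-day interval, a minor correction that alters no calculated figure. The substantive point is one of scope: a rule that closes at surgery supports the statement that the regimen does not delay surgery, but is used to conclude that it is safe/tolerable, with no later event able to affect that conclusion.

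This rests on the wording of the rule and the schedule, not on any onset distribution. The onset times in Section 3.0 show that later events are plausible enough to matter. For a single dose they are indirect evidence, and no percentage of toxicity outside the window should be claimed. The choice of surgical delay as the primary endpoint is not in question.

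**What to change.** 1. In Section 14.0, give the window as 8 to 15 days and report each patient's actual dose-to-surgery interval.
2. In Sections 1.0, 12.1 and 14.0, word a result of 5 or 6 of 6 as showing that the regimen does not delay surgery.
3. Make the statement that the regimen is safe/tolerable for further study only after the 12-week follow-up, together with the number of patients with grade 3 or higher adverse events over that period. This is a presentation requirement, not a second threshold. A numerical limit on later events would be a new decision rule for the investigators to set.
4. Reconcile the end of follow-up, which is 12 weeks after the drugs in Section 12.1 and 12 weeks after surgery in Section 14.0.

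The cost is mostly wording. Sample size, primary endpoint and pass probabilities are unchanged, and the adverse event data are already planned. The overall safety statement comes later and is narrower. If follow-up is counted from surgery, it would end 8 to 15 days later than the 12 weeks from dosing in Section 12.1 and Appendix 1, and the visit schedule would have to match.

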15.0 RESEARCH PARTICIPANT REGISTRATION AND RANDOMIZATION PROCEDURES

15.1 Research Participant Registration

Confirm eligibility as defined in the section entitled Criteria for Patient/Subject Eligibility.

Obtain informed consent, by following procedures defined in section entitled Informed Consent Procedures.

During the registration process registering individuals will be required to complete a protocol specific Eligibility Checklist.

All participants must be registered through the Protocol Participant Registration (PPR) Office at Memorial Sloan Kettering Cancer Center. PPR is available Monday through Friday from 8:30am – 5:30pm at [contact]. Registrations must be submitted via the PPR Electronic Registration System (<http://ppr/>). The completed signature page of the written consent/RA or verbal script/RA, a completed Eligibility Checklist and other relevant documents must be uploaded via the PPR Electronic Registration System.

15.2 Randomization

The study will not include any randomization.

16.0 DATA MANAGEMENT ISSUES

A Research Study Assistant (RSA) will be assigned to the study. The responsibilities of the RSA include project compliance, data collection, abstraction and entry, data reporting, regulatory monitoring, problem resolution and prioritization and coordination of activities of the protocol study team.

The data collected for this study will be entered into a secure database at MKSCC. Data from this trial will be entered in the Clinical Research Data Base (CRDB). Source documentation will be available to support the computerized patient record.

16.1 Quality Assurance

Weekly registration reports will be generated to monitor patient accruals and completeness of registration data. Routine data quality reports will be generated to assess missing data and inconsistencies. Accrual rates and extent and accuracy of evaluations and follow-up will be monitored periodically throughout the study period.

Random-sample data quality and protocol compliance audits will be conducted by the study team, at a minimum of two times per year, more frequently if indicated.

16.2 Data and Safety Monitoring

The Data and Safety Monitoring (DSM) Plans at Memorial Sloan Kettering Cancer Center were approved by the National Cancer Institute in September 2001. The plans address the new policies set forth by the NCI in the document entitled "Policy of the National Cancer Institute for Data and Safety Monitoring of Clinical Trials" which can be found at:

<http://cancertrials.nci.nih.gov/researchers/dsm/index.html>. The DSM Plans at MSKCC were established and are monitored by the Office of Clinical Research. The MSKCC Data and Safety Monitoring Plans can be found on the MSKCC Intranet at: <http://mskweb2.mskcc.org/irb/index.htm>. There are several different mechanisms by which clinical trials are monitored for data, safety and quality. There are institutional processes in place for quality assurance (e.g., protocol monitoring, compliance and data verification audits, therapeutic response, and staff education on clinical research QA) and departmental procedures for quality control, plus there are two institutional committees that are responsible for monitoring the activities of our clinical trials programs. The committees: *Data and Safety Monitoring Committee (DSMC)* for Phase I and II clinical trials, and the *Data and Safety Monitoring Board (DSMB)* for Phase III clinical trials, report to the Center's Research Council and Institutional Review Board.

During the protocol development and review process, each protocol will be assessed for its level of risk and degree of monitoring required. Every type of protocol (e.g. NIH sponsored, in-house sponsored, industrial sponsored, NCI cooperative group, etc.) will be addressed and the monitoring procedures will be established at the time of protocol activation.

17.0 PROTECTION OF HUMAN SUBJECTS

Prior to the enrollment of each patient, the risks, benefits and objectives of the study will be reviewed with the participant, including a discussion of the possible toxicities and side effects. Every effort will be made to keep study records private. Neither the patient's name nor anything else that could identify the patient will be used in any reports or publications that result from this study. Trained staff at Memorial Hospital, the Food and Drug Administration will be able to review the medical records if necessary. The patient may terminate her participation in the study at any time during the trial.

Patients will not be charged for the following costs associated with this study:

- The cost of ipilimumab and nivolumab (administration will be charged).
- Cryoablation procedure
- Research blood tests
- Research biopsy for all patients

17.1 Privacy

MSK's Privacy Office may allow the use and disclosure of protected health information pursuant to a completed and signed Research Authorization form. The use and disclosure of protected health information will be limited to the individuals described in the Research Authorization form.

A Research Authorization form must be completed by the Principal Investigator and approved by the IRB and Privacy Board (IRB/PB).

